7.1 Study Subjects

7.1.1 Disposition of Subjects

Subject disposition according to their follow-up status will be summarized. Reasons for subject discontinuations will be summarized.

7.1.2 Clinical Investigation Plan (CIP) Deviations

All CIP deviations will be summarized by type of deviation. Details of CIP deviations that affect scientific integrity or patient safety may be presented. The protocol pre-specifies a visit window of 5-7 days for the 1-week follow-up visit. The minimum required therapy evaluation period is 3 days, so the subjects could have follow-up visit starting 4-days post implant procedure. Therefore, a visit at 4-days will be allowed without requiring a deviation and data will be reported.

7.1.3 Analysis Sets

Safety Analysis set

The safety analysis set will include all subjects who meet eligibility criteria and signed the informed consent. The safety analysis set will be used for the reporting of serious AEs.

Full Analysis Set (FAS):

The FAS will include all subjects who meet eligibility criteria, signed the informed consent, and undergo the BE lead implant procedure. Subjects will be considered enrolled at the time of the BE lead procedure. The FAS will be used for reporting of the primary endpoint [REDACTED]

Additionally, it will be used for the analysis on the device, therapy, and/or procedure related AEs and DDs.

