## 9.1. Schedule of Events

### Baseline

The study-specific informed consent form must be signed prior to any study-specific procedures. Each subject must meet all inclusion and no exclusion criteria to be eligible to participate in the study. At the baseline visit, data will be gathered from subjects including relevant medical history.

The urinary voiding diary will be explained and given to the subject to be completed for a minimum of 3 consecutive days for verification of OAB (either UUI or UF). Urinary urge incontinence is defined as involuntary loss of urine associated with urgency and urinary frequency is defined as  $\geq 8$  voiding episodes per day. The diary must be completed along with confirmation that the subject is not pregnant or planning to become pregnant as part of the assessment for study eligibility.

Collection of reportable adverse events and device deficiencies will begin after the informed consent form is signed.

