7.10 Safety Evaluation

All serious, device-related, procedure-related and/or therapy-related AEs and all DDs will be considered reportable for this study. All reportable AEs and DDs will be collected throughout the study once the informed consent form is signed. AEs and DDs will be coded and summarized using the Medical Dictionary for Regulatory Affairs (MedDRA). Serious AEs will be summarized for the safety analysis set; device-related, procedure-related and/or therapy-related AEs and DDs will be summarized for all subjects who go through lead placement procedure. Summaries include the number of events, the number of subjects who experience an event, and the percentage of subjects who experienced one or more events.

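### The eligibility condition in the SAP's safety populations can drop collected adverse events from the safety tables, including, on a literal reading, events in implanted subjects

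*SAP*

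**What the plan says.** SAP 7.1.3 names two analysis sets.

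- Safety set: "The safety analysis set will include all subjects who meet eligibility criteria and signed the informed consent". Its use is stated next: "The safety analysis set will be used for the reporting of serious AEs".
- FAS: "The FAS will include all subjects who meet eligibility criteria, signed the informed consent, and undergo the BE lead implant procedure". It serves the primary endpoint, and 7.1.3 then says: "Additionally, it will be used for the analysis on the device, therapy, and/or procedure related AEs and DDs".

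SAP 7.10 returns to the same tables. For SAEs it agrees with 7.1.3: "Serious AEs will be summarized for the safety analysis set". For the other events it says: "device-related, procedure-related and/or therapy-related AEs and DDs will be summarized for all subjects who go through lead placement procedure". That wording carries no eligibility condition.

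On timing, SAP 7.10 says: "All reportable AEs and DDs will be collected throughout the study once the informed consent form is signed". Protocol 9.1 (Baseline) agrees: "Collection of reportable adverse events and device deficiencies will begin after the informed consent form is signed". Eligibility comes afterwards. Under Protocol 6.1, subjects consent first and the baseline assessment then decides whether they qualify. Under Protocol 9.1, that assessment includes a voiding diary of at least 3 consecutive days and a pregnancy check. Protocol 6.1 and 8.2 exclude those who fail. Protocol 9.9 gives a breach of, or a change in, eligibility as one example of why an investigator may end a subject's participation.

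**The concern.** A safety population is normally fixed by consent or by exposure, because an event that happened to a study subject should be tabulated whether or not the subject turns out to have met every entry criterion. Here both populations used for safety tables also require eligibility, which is decided after event collection has begun and which may be revisited after the implant.

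Two groups of subjects could be affected. The first is the implanted subject later found not to have met a criterion. This subject has been exposed to the lead and the procedure, so losing the subject's events bears directly on the safety tables. The second is the consented subject who fails screening. This subject's SAEs are collected, but the SAP gives them no population. Characterizing safety is one of the study's stated aims, so the analyst should not have to choose between readings once the events are known.

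**Working it through.** The plan gives no figure on this point. The documents contain no screen-failure count, no expected SAE rate and no count of implanted subjects found ineligible, so no numerical effect can be derived. The check is to write the populations as sets and cross them with subject status.

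Let C = signed consent, E = meets eligibility, P = underwent the lead procedure.

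- Safety set (SAP 7.1.3 and 7.10, SAEs) = C and E.
- FAS (SAP 7.1.3, related AEs and DDs) = C and E and P.
- SAP 7.10 group (related AEs and DDs) = P.

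With E read literally, as actually meeting the criteria:

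| Subject and event | SAE summary | Related AE/DD summary, 7.1.3 | Related AE/DD summary, 7.10 |
|---|---|---|---|
| Eligible, never implanted; SAE | in | does not apply | does not apply |
| Screen failure, never implanted; SAE | out | out | out |
| Implanted, later found ineligible; unrelated SAE | out | does not apply (not a related event) | does not apply (not a related event) |
| Implanted, later found ineligible; related SAE | out | out | in |
| Implanted, later found ineligible; related non-serious AE, or DD | does not apply | out | in |

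Four things follow.

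1. Among consented subjects, the FAS and the 7.10 group differ only by those in P but not in E. If no implanted subject is found ineligible, the two are identical.
2. If E means only that the subject passed screening, every implanted subject who passed is in E. The last three rows then become in wherever a summary applies, and the two sections agree.
3. The screen-failure row is out on either reading, because a screen failure by definition did not pass.
4. Exposure does not explain the condition. The safety set already admits eligible subjects who were never implanted (first row), so it is not a set of exposed subjects only.

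**The case against.** The case on the other side is substantial, and most of it stands.

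- **The safety objective is narrow.** Protocol 5.1.3 and 13.5 and SAP 4.3 confine it to the implant and the therapy evaluation. A screen failure has neither. A reader might infer that leaving out screen failures defeats the safety objective; the documents do not support that. What is left out is a background event in an unexposed subject.
- **The two SAP sections probably mean the same group.** SAP 5 defines enrollment as qualifying and undergoing the implant, SAP 7.6 treats enrolled subjects as the FAS, and Protocol 9.1 places eligibility before the procedure. SAP 7.9.1.3 and 7.9.1.4 use the same pair of wordings for the primary endpoint. A reader might infer a flat contradiction between 7.1.3 and 7.10; the text shows only a conditional difference, and 7.10 is likely shorthand.
- **Protocol 9.9 is a general list.** It allows for an eligibility breach but does not say that the subject was implanted or that the subject's data leave any set.
- **The Protocol Synopsis (Statistics) plans summary tables of reportable AEs and DDs and names no population.** A reader might infer that these events are barred from every table the study could produce. The supportable statement is that they fall outside the analysis sets the SAP names.
- **Single cases are still handled.** Protocol 11.2 and 12 have all reported events reviewed by the sponsor's medical advisor, and Table 15-1 sets reporting duties. A reader might infer that events go unreviewed or unreported; they do not.

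What survives is that the eligibility condition is a written rule in the definition of both sets. Applied as written, it can remove exposed subjects' events from safety tables. SAP 7.1.2 summarizes deviations, but that is not an adverse event table.

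**Conclusion.** The point holds as a minor one. On a literal reading, an SAE in an implanted subject later found ineligible is missing from the SAE summary, and an unrelated one is in no SAP safety population. The same subject's related AEs and DDs depend on which section the analyst follows. This rests on two assumptions: that such a subject occurs, and that the condition is applied strictly and not as having passed screening. The SAP does not say which is meant.

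The screen-failure gap needs neither assumption, but it matters less, for the reason given above.

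The size cannot be estimated from the documents and is probably small. The primary endpoint, its confidence interval and the sample size do not depend on the safety set.

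**What to change.** Remove the eligibility condition from the safety populations.

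- In SAP 7.1.3, define the safety set for SAEs as everyone who signed consent. Show SAEs in consented subjects who were never implanted in a separate listing or row, so that these subjects do not dilute the post-procedure percentage.
- In both SAP 7.1.3 and 7.10, summarize related AEs and DDs for everyone who underwent the BE lead procedure, whatever is later found about eligibility, and use the same words in both places.
- Leave the FAS for the primary endpoint as it is.

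The cost is SAP wording and one small listing. No new data are needed, because these events are already collected from consent. The change should be made before the events are tabulated, so that the population is not chosen with them in view.

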7.2 General Methodology

There is no hypothesis testing in this study.

Continuous measures will be reported as N, means, medians, standard deviations, minimums and maximums. Categorical measures will be reported in frequency distributions including counts and percentages.

For outcomes examining change from baseline, change (Δ) will be calculated as follow-up scores (S_v) minus baseline scores (S_0).

$$\Delta = S_v - S_0$$

Percent change will be calculated as 100 times the change divided by the baseline score.

$$\text{Percent change} = 100 * \Delta / S_0$$

Data analysis will be performed by Medtronic-employed statisticians or designees. A validated statistical software package will be used for the analyses of the study results (e.g. SAS version 9.4 or higher).

7.3 Center Pooling

There is no a priori provision to exclude any sites from the analysis. The data from all sites will be pooled for analysis. To reduce the possibility of atypical results from a site overly influencing the combined results, no more than 20 subjects will be implanted at each site unless the site gets pre-approval from Medtronic for additional enrollments.

7.4 Handling of Missing, Unused, and Spurious Data and Dropouts

Missing data are a potential source of bias when analyzing study data. A rigorous study design and execution will help prevent the incidence of missing data from occurring.

For the primary objective of motor or sensory response, in case subject's motor or sensory response is not tested or response data are lost during lead placement, a sensitivity analysis will be performed by displaying the full range of proportions on the potential impact of missing data by running an analysis assuming all missing values as not obtaining motor or sensory response (worst case) to all missing values as obtaining motor or sensory response (best case).

7.5 Adjustments for Multiple Comparisons

No adjustments will be made for multiple comparisons because no hypothesis testing will be conducted.

7.6 Demographic and Other Baseline Characteristics

Demographics and baseline characteristics will be summarized in the report for all enrolled subjects using the FAS.

Demographics and other baseline characteristics summarized will include:

- Age, sex, race, and ethnicity
- [REDACTED]
- [REDACTED]
- Body Mass Index (BMI) [kg/m²] = $\frac{\text{weight [kg]}}{\text{height [m]}^2}$
- [REDACTED]
- [REDACTED]
- Primary diagnosis per baseline diary (UIU, UF, both)
- Baseline leaks per day for UUI subjects (UUI subjects are defined as patients who have recorded at least one leak with urgency in their baseline diary), baseline voids per day for UF subjects (UF subjects are defined as patients who have recorded 8 or more voids per day in their baseline diary), and average degree of urgency
 - Average degree of urgency per day will be calculated based on the urgency rating where None=0, Mild=1, Moderate=2, Severe=3, and Very Severe=4 across all episodes reported per day. This will be performed separately for leaks and voids.

7.7 Treatment Characteristics

Lead implant data including motor and sensory thresholds, sensory assessment, discharge test stimulator settings, and number of leads placed (unilateral vs. bilateral) will be summarized. Motor and sensory response of the needle will also be summarized.

7.8 Interim Analyses

There is no planned interim analysis for this study.

7.9 Evaluation of Objectives

7.9.1 Primary Objective - Motor or Sensory Response

To characterize the proportion of subjects who demonstrate motor or sensory response(s) during lead placement using the InterStim BE Lead. This will be done separately for leads and the needles used to place the leads.

7.9.1.1 Hypothesis

There is no formal hypothesis.

7.9.1.2 Experimental Design

During the lead placement procedure using the InterStim BE lead, subject's motor and/or sensory response will be collected. Subjects may be implanted with more than one BE lead. In this case, the subject's motor and/or sensory response from all implanted BE leads will be recorded, and the subject will be considered as demonstrating a response if motor or sensory response is obtained from at least one BE lead.

More than one needle may be used to place the lead. In this case the subject's motor and/or sensory response from the needle used to determine final lead placement will be used. In cases where subjects have more than one lead placed, thresholds from the needles used to place each lead will be used, and the subject will be considered as demonstrating a response if motor or sensory response is obtained from at least one needle.

7.9.1.3 Analysis Methods and Presentation Format

Subjects who had the BE lead placement and provide data will be included in the primary analysis. The primary analysis will report the proportion of subjects who obtain motor or sensory response and its two-sided exact binomial 95% CI among those who had lead placement. This will be done separately for leads and the needles used to place the leads.

In cases where surgical modifications for BE leads are needed, motor or sensory response from the initial lead placement will be used for the primary analysis.

In cases where subject's motor or sensory response is not tested, or response data are lost during lead placement, or other reasons where missing data occur, a sensitivity analysis will be performed by displaying the full range of proportions on the potential impact of missing data by running an analysis assuming all missing values as not obtaining a response (worst case) to all missing values as obtaining motor or sensory response (best case).

In addition to the subject level analysis described above, a lead and needle level supporting analysis will be performed by estimating the proportion of BE Leads and needles that had motor or sensory response(s) during initial lead placement. The leads and needles that had motor or sensory responses during replacement BE lead implant will be summarized separately.

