## 9.5. Assessment of Efficacy

### Motor and sensory response

A motor or sensory response will be determined at the time of lead placement with the foramen needle and confirmed with the BE lead. Amplitude will be titrated up from 0 until a response is reported and/or observed. A sensory response is defined as the lowest amplitude where the subject first perceives sensation of the stimulation. A motor response is defined as the lowest amplitude of electrical stimulation where a motor response (e.g. bellows response, anal wink and/or plantar flexion of the big toe) is observed.

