## 11. Adverse Events and Device Deficiencies

### 11.1. Definitions/Classifications

Any adverse event meeting the definition of: serious, device related, therapy related and/or procedure related as well as all device deficiencies will be considered reportable for this study. The term “investigational device” is part of ISO 14155 definitions. The term “investigational device” refers to any device used in the study including market released devices. Adverse events and device deficiencies are defined as follows:

- Device Related: An adverse event that results from the presence or performance (intended or otherwise) of the BE lead, foramen needle or BE kit
- Procedure Related: An adverse event that occurs due to any procedure related to the implantation or surgical modification of the BE lead. The procedure is defined as the lead placement / implant procedure and surgical modification (explant procedure).
- Therapy Related: An adverse event related to therapy delivery by device e.g. device stimulation issue (normally therapy-related events resolve when the device is turned off or reprogrammed).

Adverse events that are classified as possible, probable or causal are considered to be related.

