#### **Analysis Methods**

Subjects who had the BE lead placement and provide data (completers) will be included in the primary analysis. The primary analysis will report the proportion of subjects who obtain motor or sensory response and its two-sided exact binomial 95% CI among those who had lead placement.

In cases where surgical modifications for BE leads are needed, motor or sensory response from the initial lead placement will be used for the primary analysis

In cases where subject's motor or sensory response is not tested, or response data are lost during lead placement, or other reasons where missing data occur, a sensitivity analysis will be performed by displaying the full range of proportions on the potential impact of missing data by running an analysis assuming all missing values as not obtaining a response to none of the missing values as not obtaining a response.

In addition to the subject level analysis described above, a lead level supporting analysis will be performed by estimating the proportion of BE Leads that have motor or sensory response(s) during initial lead placement. The leads that have motor or sensory responses during replacement BE lead implant will be summarized separately.

[REDACTED]

[REDACTED]

[REDACTED]

[Redacted text block]

[Redacted text block]

[Redacted text block]

[Redacted text block]

[Redacted text block]

[Redacted text block]

[Redacted text block]

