7.9.1.4 Determination of Subject for Analysis

The analysis will include all FAS subjects who provide data.

[REDACTED]

[REDACTED]

[REDACTED]

[REDACTED]

[REDACTED]

[REDACTED]

[REDACTED]

[REDACTED]

[REDACTED]

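### The primary analysis does not say how to count a procedure that ends without a lead for lack of response; read literally, that failure leaves the denominator and the proportion can only rise

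*SAP*

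**What the plan says.** Four places bear on who is in the primary denominator.

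- **Protocol 13.3, Analysis Methods:** "Subjects who had the BE lead placement and provide data (completers) will be included in the primary analysis". The exact 95% CI is taken among those with lead placement.
- **SAP 7.9.1.3:** "Subjects who had the BE lead placement and provide data will be included in the primary analysis", with the same base for the CI.
- **SAP 7.1.3:** "The FAS will include all subjects who meet eligibility criteria, signed the informed consent, and undergo the BE lead implant procedure". This set is assigned to the primary endpoint, and its definition does not require that a lead was placed.
- **SAP 7.9.1.4:** "The analysis will include all FAS subjects who provide data".

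On the order of testing, Protocol 9.5 says: "A motor or sensory response will be determined at the time of lead placement with the foramen needle and confirmed with the BE lead". Protocol 9.1 gives the same sequence for the implant procedure.

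On missing data, Protocol 13.3 and SAP 7.9.1.3 provide a worst-case to best-case analysis. It covers responses that were not tested, were lost, or are missing for any other reason.

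For a subject with more than one needle, SAP 7.9.1.2 says that the "sensory response from the needle used to determine final lead placement will be used". SAP 7.9.1.3 limits the subject-level needle proportion to needles used to place the leads.

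**The concern.** A subject tested at the needle without response, whose procedure then ends with no lead, has failed on exactly what the study sets out to measure. No visible text says whether that subject is a non-responder, is missing, or is outside the analysis. If the primary rule means that a lead was actually placed, the subject is outside. If the rule means FAS subjects who provide data, the subject may still be outside, because there is no lead response to provide.

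This matters because the study tests no hypothesis. The proportion and its interval are the whole primary result, and Protocol 6.2 says that the performance data may be used to support claims. Every subject lost by this route is a failure, so any error is upward and does not average out.

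**Working it through.** **Inputs.** SAP 6 assumes 95% response in 100 subjects who qualify for lead placement, which is 95 responders and 5 non-responders. The interval is exact binomial (Clopper-Pearson), two-sided 95% (SAP 7.9.1.3). The number of procedures ending without a lead for lack of response, k or m below, is not in the documents. The values 0 to 5 are an assumption.

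**Step 1: reproduce the plan's figure.** For x responders among n, the lower limit is the 2.5% quantile of Beta(x, n−x+1) and the upper limit is the 97.5% quantile of Beta(x+1, n−x). With x = 95 and n = 100 this gives 88.72% to 98.36%, width 9.64 points. The plan's 88.7-98.4%, width 9.6%, is reproduced.

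**Step 2: direction.** Removing k non-responders changes x/n to x/(n−k). The rise is x·k / [n(n−k)], which is positive whenever x > 0 and k ≥ 1.

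**Step 3: size when 100 subjects start and 95 respond.** Suppose k of the 5 non-responders leave without a lead and are dropped.

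| k | Reported | Exact 95% CI | Rise (points) |
|---|---|---|---|
| 0 | 95/100 = 95.0% | 88.7-98.4 | 0 |
| 1 | 95/99 = 96.0% | 90.0-98.9 | 95×1/(100×99) = 1.0 |
| 3 | 95/97 = 97.9% | 92.7-99.7 | 95×3/(100×97) = 2.9 |
| 5 | 95/95 = 100% | 96.2-100 | 95×5/(100×95) = 5.0 |

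At k = 4 the result is 95/96 = 99.0%, lower limit 94.3. So only at k = 5 does the reported interval exclude 95%.

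**Step 4: size when 95/100 is the result among subjects with a lead placed.** Add m further procedures that ended without a lead. The proportion among all started is then:

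- m = 1: 95/101 = 94.1% (87.5-97.8)
- m = 3: 95/103 = 92.2% (85.3-96.6)
- m = 5: 95/105 = 90.5% (83.2-95.3)

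All three estimates lie inside the reported interval of 88.7-98.4.

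**Step 5: does an existing analysis recover the subject?** If the k subjects are coded as missing, the worst case is 95/100 = 95.0% and the best case is (95+k)/100, which is 98.0% at k = 3. The worst case is then the right answer, but the headline stays at 95/(100−k). The subject-level needle proportion does not help, because with no lead there is no needle that was used to place one. SAP 7.7 also summarizes needle response, but it states no population and does not enter the primary proportion.

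**The case against.** The strongest reply is that lead placement is the documents' ordinary name for the procedure. Protocol 9.5 puts needle testing at the time of lead placement. Protocol 11.1 treats lead placement and implant as one procedure. SAP 7.9.1.2 speaks of the lead placement procedure. SAP 7.1.3 gives related adverse events and device deficiencies to the FAS, while SAP 7.10 says that they "will be summarized for all subjects who go through lead placement procedure", so the SAP seems to treat the two as one population. This stands, and on that reading the populations agree. It does not say how the subject without a lead is counted.

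Second, the missing-data clause reaches other reasons for missingness and could take in this subject, and SAP 7.1.1 summarizes disposition and reasons for discontinuation. Both are fair. Neither changes the primary estimate.

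Third, the objective concerns response with this lead, so a needle-only failure could be seen as procedural rather than as lead performance. That is a reason to keep the lead-placed proportion, but as a supporting analysis beside one that counts everyone started.

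Fourth, the triggering event is assumed. No visible text says that lack of needle response ends a procedure without a lead. The implant manual is not supplied, and parts of Protocol 9.1, 13.1.1 and 13.3 and the text after SAP 7.9.1.4 are redacted. This stands and limits what can be said about size.

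A reader might infer that the plan deliberately discards failures, or that subjects with a lead placed but no response are dropped. The documents support neither: those subjects count as non-responders on either reading.

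**Conclusion.** The concern holds as a minor point about an unclassified outcome. Protocol 13.3 and SAP 7.9.1.3 state a rule that, taken literally, removes a procedure ended for lack of response from the primary denominator. The condition on providing data in SAP 7.9.1.4 could do the same. The direction is certain: upward only. The size is unknown: zero if every procedure ends with a lead, 1.0 point for one such subject in 100, and at most 5.0 points under the plan's assumed 95%. The maximum requires every expected non-responder to leave without a lead, which nothing in the documents supports as likely.

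Two stronger readings should be resisted. One is that the reported figure will be biased; that needs both the literal reading and at least one such procedure. The other is that a single FAS denominator would settle the matter; the SAP already names the FAS, and the gap remains. No decision threshold is visible, so the consequence is an estimate that may be too favorable, not a changed decision.

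**What to change.** Align Protocol 13.3, SAP 7.9.1.3 and SAP 7.9.1.4 on one rule, before the data are seen:

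1. The primary denominator is all FAS subjects in whom the procedure was started.
2. A procedure that ended without a lead for lack of response counts as non-response.
3. Missing is reserved for response not tested or data lost, handled by the existing worst-case and best-case analysis.
4. The rule that a response from at least one lead suffices stays as it is for subjects with a lead placed.
5. The subject-level needle proportion follows the same rule, so that a subject with no lead is not lost for want of a qualifying needle.
6. The number of procedures ending without a lead, and the reasons, are reported.
7. The proportion among subjects with a lead placed is kept as a supporting analysis of the lead itself.

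The cost is a reported proportion that may be slightly lower. If the change counts as a principal feature (Protocol 13.1, SAP 7.11), it needs a protocol and SAP amendment, with IRB/EC submission for the protocol (Protocol 15.12). A small form change may also be needed; the form is not in the documents. No extra subjects or visits are required, and clinical management is untouched.

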6. Characteristics indicating a poor understanding of the study or characteristics that indicate the subject may have poor compliance with the study protocol requirements
7. Concurrent participation in another clinical study that may add additional safety risks and/or confound study results.*

*Subjects in concurrent studies can only be enrolled with permission from Medtronic. Please contact Medtronic's study manager to determine if the subject can be enrolled in both studies.

The following will be conducted:

1. Baseline
2. Enrollment / Basic Evaluation Lead Implant Procedure
3. Therapy Evaluation
4. One Week Follow-up Visit (Study Exit)

6. Determination of Sample Size

Subjects will be enrolled to obtain a sample size of approximately 100 subjects who complete a BE lead placement with motor or sensory threshold testing to confirm clinical performance. The sample size of approximately 100 subjects is driven to obtain precision of the primary endpoint. Assuming that motor or sensory response is able to be obtained in 95% of subjects who qualify for a BE lead placement, with 100 subjects, this produces a two-sided 95% Confidence Interval (CI) of 88.7-98.4% with a width equal to 9.6%. The CI width will vary slightly depending on the actual proportion of subjects with motor or sensory responses.

7. Statistical Methods

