7.11 Changes to Planned Analysis

Any changes to the data analysis methods described in the SAP will require an amendment only if it changes a principal feature of the SAP. Any other change to the data analysis methods described in the SAP, and the justification for making the change, will be described in the clinical study report.

8. Validation Requirements

Statistical programming code that affects the result of the main analysis (e.g., not including sensitivity or supporting analyses) for the primary objective shall be validated using Level I validation, which is defined as the peer reviewer independently programs output and then compares the output with that generated by the original Statistical Programmer.

Programming code for randomization and programming code that affects the result of the main analysis for the secondary objective(s) shall be validated using at least Level II validation. In addition, those main statistical analyses that are planned for publication and have not been previously validated should be validated using at least Level II validation. The CIP deviation summary shall be validated using at least Level III validation and the high-level adverse event summary shall be validated using at least Level II validation. Additional measures where a p-value or confidence interval has been generated (eg, Motor or Sensory Response of the Needles) shall be validated using at least Level II validation.

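### Does the needle-level supporting proportion lack a denominator, and is needle response primary or additional?

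*SAP*

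**What the plan says.** SAP 7.9.1 extends the primary objective to needles: "This will be done separately for leads and the needles used to place the leads". SAP 7.9.1.3 repeats that limit for the subject-level proportion and its exact 95% interval. Three paragraphs later it adds that "a lead and needle level supporting analysis will be performed by estimating the proportion of BE Leads and needles" with a response at initial placement, this time without restricting the needles to those that placed a lead.

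SAP 7.9.1.2 deals with multiple needles. It notes that "More than one needle may be used to place the lead" and rules that the "response from the needle used to determine final lead placement will be used". With two leads, the needle that placed each one counts, and one responding needle makes the subject a responder. For leads, the "response from all implanted BE leads will be recorded"; there is no matching sentence for needles tried and set aside.

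SAP 8 requires Level I validation for the main primary analysis and at least Level II for "Additional measures where a p-value or confidence interval has been generated (eg, Motor or Sensory Response of the Needles"). SAP 7.7 also lists needle response among treatment characteristics. In the protocol, the primary objective (5.1.1 and 13.3) names only the lead, and the supporting analysis is lead level only: "a lead level supporting analysis will be performed by estimating the proportion of BE Leads that have motor or sensory response(s".

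**The concern.** Foramen needle performance is part of the study purpose (Protocol 4.2), so a needle-level percentage will be read as a device result. The supporting sentence in SAP 7.9.1.3 can be taken to cover every needle tested or only those that placed a lead. If operators try needles until one responds, placing needles are selected for success and the all-tested percentage would normally be lower. Two analysts could then report different figures from the same data, or the choice could follow sight of the results. On the placing-needle reading the analysis also seems redundant: in a one-lead subject the needle-level and subject-level results are identical.

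The label raises a second question. SAP 7.9.1 appears to make needle response a second primary result, whereas SAP 8 treats it as additional and SAP 6 speaks of one endpoint: "The sample size of approximately 100 subjects is driven to obtain precision of the primary endpoint". A reader may ask which result is primary and which validation level applies.

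**Working it through.** **1. The plan's own figure.** Inputs from SAP 6: 95% response, 100 subjects, so x = 95 and n = 100. The exact (Clopper-Pearson) limits are the 2.5% quantile of Beta(x, n - x + 1) = Beta(95, 6) and the 97.5% quantile of Beta(x + 1, n - x) = Beta(96, 5). These are 88.72% and 98.36%, a width of 9.64 points, matching the stated 88.7-98.4% and 9.6%. No needle count enters this calculation.

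**2. Which needles count.** The visible text on this objective, in order:

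- SAP 7.9.1: needles used to place the leads.
- SAP 7.9.1.2: the needle that determined final placement; with two leads, the placing needle for each.
- SAP 7.9.1.3, primary sentence: needles used to place the leads.
- SAP 7.9.1.3, supporting sentence: needles, unqualified.

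Three statements specify placing needles, the fourth omits the qualifier, and no visible passage introduces a set of all tested needles. Protocol 9.5 also pairs the two devices: response is found with the needle, then confirmed with the lead.

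**3. Redundancy.** Suppose 100 subjects, of whom b receive two leads (Protocol 7.1 allows up to two). There are then 100 + b leads and, on the placing-needle reading, 100 + b needles. Each count differs from the 100 subjects only through b. The lead-level analysis therefore repeats the subject-level result in one-lead subjects just as the needle-level analysis does. Redundancy is no argument for the all-tested reading.

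**4. Size under assumptions.** Assume 100 one-lead subjects and 95 responding placing needles (the 95% is borrowed from the lead endpoint). Let a further needles be tried, of which r respond. Placing needles only: 95/100 = 95.0%. All tested: (95 + r)/(100 + a).

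| Extra needles a | r = 0 | r = a/2 | r = a |
|---|---|---|---|
| 0 | 95.0% | 95.0% | 95.0% |
| 10 | 95/110 = 86.4% | 100/110 = 90.9% | 105/110 = 95.5% |
| 20 | 95/120 = 79.2% | 105/120 = 87.5% | 115/120 = 95.8% |

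For up to 20 extra needles the gap runs from 79.2 - 95.0 = -15.8 to 95.8 - 95.0 = +0.8 points. With two or three needles tried on every lead and no discarded needle responding, the result would be 95/200 = 47.5% or 95/300 = 31.7%; if discarded needles also responded 95% of the time it would be 95.0%. The spread comes entirely from a and r, which the documents do not give. The kit in Protocol Table 7-1 holds three needles (two of 8.8 cm, one of 12.6 cm), but that is what is packed, not what is tried.

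**5. The label.** Level I meets the requirement for the primary main analysis and also the minimum of Level II for additional measures, so one programming decision satisfies both sentences of SAP 8. SAP 7.2 states that no hypothesis is tested and SAP 7.5 that no multiplicity adjustment is made, so no error rate depends on the label. SAP 4.1, like Protocol 5.1.1, names only the lead, which indicates the primary result.

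**The case for a change.** The strongest reply is that the rule in SAP 7.9.1.2 concerns the subject's response and ends by classifying the subject, while SAP 7.9.1.3 introduces the needle-level analysis as something beyond the subject level. Nothing says that the rule carries over. Since SAP 7.9.1.2 recognises that several needles may be used for one lead, the two denominators can differ in practice, and the protocol cannot settle the matter because it has no needle-level analysis.

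That is right as a reading of the words. The supporting sentence is looser than its neighbours, and the labels in SAP 7.9.1 and SAP 8 do differ. But an unrepeated qualifier is weak evidence of a different intention when the surrounding section defines the relevant needle. Either denominator gives a valid descriptive proportion if the table names the needles counted. The risk of choosing after the data are seen is small: there is no threshold to pass, and SAP 7.11 requires a change in method to be justified in the study report or made by amendment.

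Reporting needles tried per lead or first-needle response would be informative, but these are additional outputs. Whether discarded needles are recorded depends on a case report form that is not among the documents.

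**Conclusion.** No change follows. The missing qualifier is a gap that an analyst fills sensibly from SAP 7.9.1, 7.9.1.2 and the first paragraph of 7.9.1.3 by counting the placing needle of each initially placed lead. The differing label is a clerical inconsistency without effect on validation, inference or the identity of the primary lead result.

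Only a supporting, descriptive needle percentage could move. The illustrated gap of -15.8 to +0.8 points assumes one lead per subject, 95 of 100 responding placing needles and at most 20 extra needles; other assumptions widen it, and it vanishes with one needle per lead. The conclusion rests on the visible text. Redacted material follows the primary objective in both documents and follows SAP 7.9.1.4, but the sections that set up this analysis can be read.
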